Since its introduction, low-molecular-weight heparins (LMWHs) are still common used in practice as thromboprophylactic agent. But, they require subcutaneous administration which making it challenging for use in settings other than the inpatient one. Despite the lower incidence of low-molecular-weight heparins (LMWHs) induced heparin-induced thrombocytopenia (HIT) compared with unfractionated heparins (UFH) in the postoperative setting, the risk of LMWH induced HIT in patients treated for VTE still concerns many clinicians. In addition to its subcutaneous administration, fondaparinux is contraindicated in severe renal impairment patients (with creatinine clearance (CrCl) <30 milliliter/minute) and those who have low body weight (<50 kg; VTE prophylaxis only). While available orally, Vitamin K antagonists (VKAs) like Warfarin have unpredictable pharmacologic effects requiring a wakeful monitoring. Warfarin is also a remarkable source of food and drug interactions. As a result, it is mandatory to search for novel drugs or at least to search for new indications of really existing drugs. [2]

In July 2011, the Food and Drug Administration (FDA) approved an orally administered selective factor Xa inhibitor called Rivaroxaban for the prevention of deep vein thrombosis (DVT) after total hip replacement (THR) or total knee

replacement (TKR) surgeries. According to the Regulation of Coagulation in Orthopedic Surgery to Prevent Deep Vein Thrombosis and Pulmonary Embolism (RECORD) trials, rivaroxaban demonstrated superiority to enoxaparin in reducing venous thromboembolism without significant increase of bleeding risk. Rivaroxaban is recommended to be used at a fixed dose of 10 mg daily, with or without food, for 35 days following THR or 12 days following TKR. [3]

Although the US Food and Drug Administration (FDA) advisory committee has recommended approval of rivaroxaban, many questions have been raised on the Regulation of Coagulation in Orthopedic Surgery to Prevent Deep Vein Thrombosis and Pulmonary Embolism (RECORD) trials of rivaroxaban. Some may argue that dosing was inconsistent with the recommendations. Others went far to say that the duration of treatment was inconsistent and did vary with enoxaparin. In other words, it was somewhat short.

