It is proposed to randomly assign at least 100 patients sequentially based on admission; in a single blind, interventional trial, to two separate groups. Patients are going to be selected from our university teaching hospital. patients were randomly assigned to a study group with the use of permuted blocks and stratification using well trusted randomization websites or software programs (SAS). Permuted block randomization list will be transferred from alphabetic symbol by the competent orthopedic supervisor and coded based on the randomization order by manual coding preset by orthopedic supervisor [5]. Double dummy technique may be feasible here as long as we tackled difficulty of providing syringes containing saline. However, the risk of injecting a saline solution subcutaneously (i.e. bleeding complications may develop in persons taking an anticoagulant agent plus unnecessary injections) may outweigh the benefit. Since the investigator do not know which therapy is administrated, the potential for the results to be biased is minimized [6].

The first group is to be on rivaroxaban with dosage according to the orthopedic approved regimen (10 mg once daily 6-10 hours after the surgery; recommended total duration of therapy: 12 to 14 days; ACCP recommendation: Minimum of 10 to 14 days; extended duration of up to 35 days suggested (Guyatt 2012).[3]

The other group will be administered the standard of care (SOC) enoxaparin. Dosage and duration of therapy are illustrated in Table 1 [2].

Drug	Dosage and Duration
Enoxaparin	Once-daily dosing: 40 mg once daily, with initial dose within 9 to 15 hours before surgery, and daily for at least 10 days (or up to 35 days postoperatively) or until risk of DVT has diminished or the patient is adequately anticoagulated on warfarin. The American College of Chest Physicians recommends initiation ≥ 12 hours preoperatively or ≥ 12 hours postoperatively; extended duration of up to 35 days suggested (Guyatt, 2012).

Table 1: *Dosing of SOC drugs used in thromboprophylaxis after orthopedic surgery.*

It is expected here that all medication will be taken for a duration of 10 days after surgery. The type, duration and dose of the thromboprophylactic agents will be discussed with and determined by the competent physician before saying a particular patient can be enrolled.

Study population

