The primary efficacy outcomes are the composite of any deep-vein thrombosis, nonfatal pulmonary embolism, or death up to 30 days. The main secondary efficacy outcome is major venous thromboembolism, which is defined as the composite of proximal deep-vein thrombosis, nonfatal pulmonary embolism, or death from venous thromboembolism.

The main safety outcome is the incidence of major bleeding beginning after the first dose of the study drug and up to 2 days after the last dose of the study drug (on-treatment period). Major bleeding is defined as bleeding that is fatal, occurs in a critical organ (e.g., retroperitoneal, intracranial, intraocular, and intraspinal bleeding), or requires reoperation or extra surgical-site bleeding that was clinically overt and is associated with a fall in the hemoglobin level of at least 2 g per deciliter or that requires transfusion of 2 or more units of whole blood or packed cells. Other safety outcomes include any on-treatment bleeding, any on-treatment non- major

bleeding, hemorrhagic wound complications (a composite of excessive wound hematoma and reported surgical-site bleeding), any bleeding that starts after the first oral dose of rivaroxaban and ended up to 2 days after the last dose is administered, adverse events, and death.

Validated clinical prediction rule is recommended to estimate pretest probability of venous thromboembolism. Duplex ultrasonography is the preferred test to diagnose DVT [7]. Many prediction scales are available like *Wells Clinical Models for Evaluating the Pretest Probability of VTE*.

Symptoms and signs of DVT may include unilateral leg swelling, pain in the affected leg, calf tenderness in affected leg, increased leg warmth, erythema of affected leg, or a “palpable cord” may be felt in the affected leg.

Regarding PE, diagnosis is suspected in patients with dyspnea, tachypnea, pleuritic chest pain, cough, and/or fever. Diagnosis begins with initial risk stratification based on presence of shock or persistent hypotension to identify patients at high risk of early mortality.

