For patients with suspected high-risk PE with shock or hypotension, emergency computed tomography(CT) angiography beside transthoracic echocardiography is recommended depending availability and clinical circumstances. While for patients not suspected of having high-risk PE, clinical assessment of likelihood of PE using validated prediction rules and clinical judgement to distinguish between low and high-risk PE may use [8]. However, PE can be diagnosed based on computed tomography pulmonary angiography (CTPA). CT pulmonary angiography is preferred method when available.

It is recommended to have baseline Scr and platelets count. Based on Heparin induced thrombocytopenia, it is advisable to monitor platelets count beginning of the fourth day and every three days until discontinue of Heparins.

Data analysis

The patients in the two groups will be matched in advance for the difference in Patients’ characteristics, VTE risk factors, history of VTE, types of surgery, types of anesthesia and duration of surgery. This ensures fair randomization between groups. Statistical analysis will be performed at an overall significance level of 0.05, adjusted for the primary and secondary end points using non- independent t-test

(SPSS software). Comparisons of the primary end points between treatment groups were performed by means of a log-rank test. To estimate the size of the effect, we will use a Cox regression model. On the other hand, the cost-effective analysis (CEA) will be based mainly on estimating the average cost-effective ratio(ACER) and the incremental cost for each additional cure.

References

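### The plan relies on investigator masking to limit bias, but describes no procedure that would mask anyone to a tablet versus an injection

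*Combined protocol and SAP*

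**What the plan says.** Under Study design and randomization, patients are to be allocated "in a single blind, interventional trial, to two separate groups". That sentence does not say who is blind. The section then describes a permuted-block list that the orthopedic supervisor converts and codes. It next turns to a double dummy: "Double dummy technique may be feasible here as long as we tackled difficulty of providing syringes containing saline". The following sentence leans the other way, beginning "However, the risk of injecting a saline solution subcutaneously" and concluding that this risk may exceed the benefit. No double dummy is adopted. The paragraph closes with the claim at issue: "Since the investigator do not know which therapy is administrated, the potential for the results to be biased is minimized".

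The two treatments differ in route. The background says of low-molecular-weight heparins that "they require subcutaneous administration". The safety outcomes under Outcome measure and follow up refer to "any bleeding that starts after the first oral dose of rivaroxaban".

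That section also sets out how events are found. For venous thromboembolism, "Validated clinical prediction rule is recommended to estimate pretest probability of venous thromboembolism". Several scales are said to exist and one is given as an example, but none is selected and no threshold is set. Duplex ultrasound is the preferred test for DVT and CT pulmonary angiography for PE. For heparin-induced thrombocytopenia, "it is advisable to monitor platelets count beginning of the fourth day and every three days until discontinue of Heparins".

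**The concern.** The plan gives investigator masking as its reason for expecting little bias, so it should be possible to see how that masking is achieved. A tablet and a subcutaneous injection are distinguishable to the patient and to whoever gives them unless both groups receive both forms, and the plan argues against that.

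The outcomes are of a kind for which masking matters. If testing follows clinical suspicion, anyone who knows the arm and takes part in the work-up can, without intending to, refer more readily in one arm than the other. The same applies to reporting of wound bleeding. Unequal detection of this kind looks like a treatment effect and does not shrink as the sample grows. A report that repeated the masking claim would credit the results with a safeguard the trial may not have had.

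**Working it through.** The plan gives no figure for masking or detection, so there is nothing to reproduce. The main check sets the passages side by side.

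**1. What could deliver the masking?**

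| Feature of the plan | Does it hide the arm? |
|---|---|
| Single-blind label | Names no masked party |
| Supervisor codes the randomization list | Can conceal the sequence; cannot hide the route once treatment starts |
| Double dummy | Would hide the route, but is not adopted |
| Masked imaging reader, assessor or adjudicator | None described |

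**2. What could reveal the arm?**

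- Route: oral against subcutaneous. This is the decisive cue for the patient and treating staff.
- Serial platelet counts: tied to heparin use, so they may reveal the arm. They are advised rather than required, and the baseline count is not limited to one arm.
- Start of dosing: a weaker cue. Rivaroxaban is to start 6–10 hours postoperatively. The enoxaparin regimen listed first in Table 1 starts 9–15 hours preoperatively, but the table also cites a guideline option of a postoperative start. Timing therefore need not separate the arms.

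**3. Which outcomes are exposed?**

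- DVT and PE: exposed, because work-up runs through symptoms, prediction rules and clinical judgement, and no imaging is scheduled.
- Wound complications: exposed, because they include surgical-site bleeding that is reported.
- Major bleeding: partly exposed. Reoperation and transfusion are clinicians' decisions; fatal or critical-organ bleeding and a hemoglobin fall of 2 g/dL leave less room for judgement.
- Death: little exposed.

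**4. Illustration of size.** All event and detection rates here are assumptions.

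Observed risk = true risk × proportion of events detected. With a true DVT risk of 10% in both arms:

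- Detection 60% and 40%: 0.10 × 0.6 = 0.06 and 0.10 × 0.4 = 0.04; ratio 0.06/0.04 = 1.5.
- Detection 70% and 50%: 0.10 × 0.7 = 0.07 and 0.10 × 0.5 = 0.05; ratio 0.07/0.05 = 1.4.

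The true risk cancels, so the false ratio is simply the ratio of the detection proportions.

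The second illustration is the chance of a false positive. It assumes 50 patients per arm (the plan says at least 100 in total and gives no allocation ratio), a two-sided 0.05 level (the plan gives 0.05 overall), no true difference, full detection in one arm and reduced detection in the other. It enumerates a pooled two-proportion z test exactly. That is a simple stand-in for the log-rank comparison named under Data analysis.

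| True event rate | Other arm 100% detected | 75% | 50% |
|---|---|---|---|
| 5% | 0.0434 | 0.0494 | 0.0754 |
| 10% | 0.0506 | 0.0694 | 0.1447 |
| 20% | 0.0522 | 0.1057 | 0.3027 |
| 30% | 0.0498 | 0.1368 | 0.4425 |

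At low event rates with a modest detection gap, the error rate barely moves. It becomes serious only when events are common or the gap is wide.

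**The case against.** The strongest reply is that a double dummy is needed to mask patients and the staff giving the drug, not necessarily the investigator. The protocol names an orthopedic supervisor, a competent physician and the investigator separately. An investigator kept away from dosing could be masked without any dummy, and the paragraph can be read that way. This stands as far as it goes. A reader might infer that masking the investigator is impossible here, or that the plan flatly contradicts itself. The documents do not support that: they leave the procedure out rather than rule it out. But the separation is not described either, so the reply asks the reader to supply what the plan should state.

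A second reply is that nothing says who applies the prediction rule or orders imaging. That also stands. It is an inference that people who know the arm will decide who is tested, though the plan gives the task to no one else. Similarly, the exclusion of patients who cannot undergo bilateral venography hints at systematic imaging, which would remove much of the referral problem for DVT. No venography is scheduled, however, and duplex is the stated preference.

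Third, the numbers are hypothetical. With 50 per arm, 6% versus 4% is 3 events against 2, which by itself would change no conclusion. That is correct, and the illustrations should be read only as showing the mechanism and its range.

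Finally, the physician's role in determining the agent precedes enrollment, so it does not show that the physician knows the allocated arm. I place no weight on it.

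**Conclusion.** The point holds in this form: the plan claims protection from bias through investigator masking, and no procedure it describes provides that protection. Confidence in this is high, because it rests on the text alone.

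The consequence is a risk of unequal detection of DVT, PE and some bleeding. Its direction and size cannot be determined from the documents. Under the assumptions shown, false risk ratios of 1.4 to 1.5 arise from detection gaps of 20 percentage points, and the false-positive rate ranges from essentially nominal (0.0494) to 0.4425. A reader might go further and conclude that the results will be biased, or that the primary and safety outcomes are compromised as a whole. The documents do not support either: death and the more objective parts of the major-bleeding definition are less exposed, and no detection rates are given. The sponsor should correct this before the trial is reported as masked.

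**What to change.** 1. Withdraw the statement that investigator masking minimizes bias, or restrict it to named roles that are actually masked and say how.
2. Describe treatment as open to patients and treating staff. A single-blind label can stay only if the masked party is identified.
3. Leave the study drug off ultrasound and CT requests so that the existing readers are masked. This protects interpretation of the images, not the decision to order them.
4. To address that decision and the reporting of bleeding, use one symptom and bleeding checklist on the same days in both arms.
5. Prespecify one work-up rule for suspected DVT and PE and apply it identically in both arms. Its content is for the investigators to choose.

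The cost is revised protocol wording, one form, a change to the imaging request and a less favourable design label. Completing the checklist takes some staff time, which the documents give no basis for estimating. No sham injections are needed, so the sponsor's own reservation about saline injections is respected.

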The Patients >18 years who are going to be scheduled to undergo orthopedic surgery in whom decision of thromboprophylaxis taken will be enrolled for inclusion.

Exclusion criteria are based on the approved contraindication listed, for all drugs used, in the drug’s labels and supplemented by data from well trusted compendia like Lexi comp® or Micromedex®. The exclusion criteria are as follows, but not limited to:

- I. Severe hypersensitivity to drugs or any component of the formulation.
- II. Planned intermittent pneumatic compression
- III. A requirement for anticoagulant therapy that could not be stopped
- IV. Severe hypersensitivity reaction (eg, anaphylaxis) to rivaroxaban or enoxaparin.
- V. Received another anticoagulant for more than 24 hours
- VI. Active bleeding or a high risk of bleeding
- VII. Thrombocytopenia associated with a positive test for antiplatelet antibody.
- VIII. Warfarin associated INR more than 1.5 on the day of the surgery
- IX. Conditions preventing bilateral venography
- X. ICU stay after surgery
- XI. Pregnant or breast-feeding

- XII. Creatinine clearance less than 30 ml per minute or acute renal failure before the surgery or at any point during the study period.
- XIII. Moderate or Severe (Child Pugh B or C) hepatic Impairment or in patients with any hepatic disease associated with coagulopathy.
- XIV. Concomitant use of drugs that are both p-glycoprotein inhibitors and moderate to strong cyp3a4 (ketoconazole, itraconazole, lopinavir/ritonavir, ritonavir, indinavir/ritonavir & conivaptan)
- XV. CrCl 15 to 80 mL/min PLUS both P-glycoprotein inhibitors and moderate CYP3A4 inhibitors (eg, abiraterone acetate, diltiazem, dronedarone, erythromycin, verapamil)

The study draft will be submitted to our ethics committee attached to the hospital administration board before enrollment of patients.

Prescribed co-medication of interest.

Because of the well documented effect of drugs affecting CYP3A4 co-prescribed with rivaroxaban, strong inhibitor and inducers listed on <http://medicine.iupui.edu/clinpharm/ddis/clinical-table/> under the guidance of US Food and Drugs Administration(FDA) are contraindicate with rivaroxaban. Patient on these interacting drugs will be excluded.

Outcome measure and follow up.

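### The exclusion list is open and two of its criteria can act after assignment, yet no analysis population keeps removed patients in the comparison

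*Combined protocol and SAP*

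**What the plan says.** All references are to the combined protocol and SAP.

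**Study population.** The source of the exclusions is given first: "Exclusion criteria are based on the approved contraindication listed, for all drugs used, in the drug’s labels and supplemented by data from well trusted compendia". The numbered list is then opened with "The exclusion criteria are as follows, but not limited to". Fifteen criteria follow. Two of them can be met after a patient has been assigned:

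- Criterion X: "ICU stay after surgery".
- Criterion XII, which besides low creatinine clearance covers "acute renal failure before the surgery or at any point during the study period".

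**Study design and randomization.** Patients are allocated "in a single blind, interventional trial, to two separate groups". Rivaroxaban is described as "10 mg once daily 6-10 hours after the surgery". Table 1 lists enoxaparin "with initial dose within 9 to 15 hours before surgery", and also cites a guideline that allows a start before or after the operation. The section says that the investigator does not know the treatment. It also argues that the risk of saline injections may exceed the benefit of a double dummy, and has the orthopedic supervisor code the randomisation list.

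**Data analysis.** The primary comparison is a log-rank test, with a Cox model for the size of the effect. No analysis population is named, and no rule covers patients excluded after randomisation.

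**The concern.** Randomisation makes the groups comparable at the moment of assignment. They stay comparable only if everyone assigned is kept in the analysis, or if any losses are unrelated to arm and outcome. Three features of the plan work against this together: a list to which reasons can be added, listed criteria that can be met after assignment, and no statement of who is analysed.

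If removals are related to both arm and outcome, the risk ratio shifts and the test no longer holds its 5% level. A reader of the final report could not detect this, because the plan does not ask for exclusions to be logged or reported by arm.

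**Working it through.** The plan gives no event rate, power or effect size behind its figure of at least 100 patients, so there is no stated number to reproduce. The check has two parts.

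**1. Reading the passages together**

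- *Does the reference to labels and compendia close the list?* No. Criteria II (planned pneumatic compression), IX (conditions preventing bilateral venography) and X (intensive care after surgery) are not evidently drug contraindications. The list already goes beyond its stated source.
- *Can exclusion follow assignment?* Yes. Criterion XII says so for renal failure. Criterion X can be known only after surgery. If enoxaparin starts before surgery, as the first entry in Table 1 has it, assignment must already have been made and a first dose may have been given. A rivaroxaban patient has had no dose at that point.
- *Can removal depend on arm?* Yes, in two ways. The person judging an exclusion may know the treatment. And where one drug starts before surgery and the other after, early treatment could itself influence who meets criterion X.
- *Does the analysis put removed patients back?* Nothing in Data analysis says so.

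**2. Size, under assumptions**

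From the plan: about 100 patients, two groups, significance level 0.05. Assumed: 50 per arm, a two-sided test, the same true event rate *p* in both arms, and each would-be event patient in one arm removed with probability *q*.

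Expected number removed = 50 × *p* × *q*

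Apparent risk ratio = (1 − *q*) / (1 − *p* × *q*)

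For example, *p* = 0.10 and *q* = 0.40 give 50 × 0.10 × 0.40 = 2 removed and 0.60 / 0.96 = 0.625. With *p* = 0.20 and *q* = 0.40, the results are 4 removed and 0.60 / 0.92 = 0.652.

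Type I error comes from 200,000 simulated trials per row, using a chi-square test on the proportions as a stand-in for the log-rank test.

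| Event rate *p* | Removal *q*, one arm | Expected removed | Apparent risk ratio | Type I error |
|---|---|---|---|---|
| 5% | 0 | 0 | 1.00 | 4.3% |
| 5% | 20% | 0.5 | 0.81 | 4.8% |
| 5% | 40% | 1 | 0.61 | 6.2% |
| 10% | 0 | 0 | 1.00 | 5.1% |
| 10% | 20% | 1 | 0.82 | 6.0% |
| 10% | 40% | 2 | 0.63 | 9.6% |
| 20% | 0 | 0 | 1.00 | 5.3% |
| 20% | 20% | 2 | 0.83 | 7.1% |
| 20% | 40% | 4 | 0.65 | 14.8% |

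As a control, removing 20% of would-be events from *both* arms leaves the type I error at 5.3% (*p* = 10%) and 5.1% (*p* = 20%). The harm comes from removal that differs by arm, not from removal as such.

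**The case against.** **The list is bounded.** The sentence before it ties exclusions to labels and compendia, so the open wording may mean no more than further contraindications from those sources. This stands in part: unlisted reasons are not wholly free. But criteria II, IX and X show that the source is not a limit.

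**The team is masked.** A reader might infer from the tablet-versus-injection comparison that whoever applies exclusions is unmasked. The documents do not establish that, because they say that the investigator does not know the treatment. They do not assure masking either, given the single-blind label, the argument against a double dummy and the supervisor's coding of the list.

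**Exclusion happens before enrolment.** The plan says that the type, duration and dose of the agents "will be discussed with and determined by the competent physician before saying a particular patient can be enrolled". That sentence concerns the drug regimen, not the exclusion list, so it neither limits the timing of exclusions nor confirms that the list is open. Equally, a reader might infer that unlisted reasons may be applied at any time. That would rest on silence: the plan sets no time for them. Exclusion after assignment is explicit only for part of criterion XII, and follows for criterion X from when it can be known.

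**Open exclusion harms only generalisability.** This is correct for exclusion before a concealed assignment. It does not hold for removal afterwards.

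**The numbers can be made dramatic.** Two event patients taken from one arm of an assumed 3/50 versus 3/50 turn a risk ratio of 1.0 into (1/48) / (3/50) = 0.35. That is a chosen worst case, and the two-sided Fisher p-value is about 0.62. The estimate moves, but no treatment difference is established.

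**Conclusion.** The point holds for removal after assignment. The open list, criteria X and XII and the missing analysis population together permit removals that can depend on arm, and the plan contains no safeguard against this.

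The effect is moderate and depends on unstated quantities. At assumed event rates of 10% to 20% with 50 per arm, losing about one or two would-be event patients from one arm (*q* = 20%) gives a risk ratio of 0.82 to 0.83 and a type I error of 6.0% to 7.1%. Losing about two to four (*q* = 40%) gives 0.63 to 0.65 and 9.6% to 14.8%. These figures assume that only event patients are removed, and from one arm only. They show what the plan allows, not what will happen.

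A reader might go further and conclude that the population the result applies to cannot be stated. The documents do not support that: they give an age limit, a surgical setting, a decision to give thromboprophylaxis and fifteen criteria. The open wording blurs the edge of that population without leaving it undefined.

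**What to change.** 1. Delete the words that leave the list open. Define the complete set as the listed criteria plus the labelled contraindications of either drug in force at trial start.
2. Apply that set to every patient before the assignment is opened. Log each screened but excluded patient by criterion number.
3. Treat conditions that arise after assignment (criterion X and the on-study part of criterion XII) as reasons recorded during follow-up, not as exclusions from the analysis. Closing the list does not deal with these two, because they cannot be fully settled beforehand.
4. State in Data analysis that all randomised patients are followed to day 30 and analysed as randomised in the log-rank and Cox analyses, with post-assignment conditions reported by arm.

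The clinical handling of these patients is a separate matter and is not addressed here.

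Cost: a few sentences, a screening log, and follow-up to day 30 of patients who would otherwise have been dropped. The downside is less flexibility, since an unforeseen reason for exclusion would need a dated amendment. Labelled contraindications remain covered throughout.

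### With a pre-operative enoxaparin start, the day-of-surgery INR in exclusion VIII can come after the first dose, and must for early operations: a minor, cheaply fixed safety gap in one arm

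*Combined protocol and SAP*

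**What the plan says.** Exclusion VIII, under Study population, is "Warfarin associated INR more than 1.5 on the day of the surgery". The lead-in to the list says that the exclusions rest on contraindications in the drug labels, and adds "The exclusion criteria are as follows, but not limited to".

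The first-dose times are under Study design and randomization:

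- Rivaroxaban is given "10 mg once daily 6-10 hours after the surgery".
- Enoxaparin in Table 1 is "40 mg once daily, with initial dose within 9 to 15 hours before surgery". The same cell reports that the chest physicians' guideline "recommends initiation ≥ 12 hours preoperatively or ≥ 12 hours postoperatively".
- No enoxaparin start is fixed for the trial: "The type, duration and dose of the thromboprophylactic agents will be discussed with and determined by the competent physician", and this happens before a patient is enrolled.

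Two other exclusions concern earlier anticoagulation: III, "A requirement for anticoagulant therapy that could not be stopped", and V, "Received another anticoagulant for more than 24 hours". Exclusion VI covers active bleeding or high bleeding risk.

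The only baseline laboratory tests named, under Outcome measure and follow up, are serum creatinine and platelet count. The protocol states no INR before the day of surgery, no warfarin washout, and no rule that the INR must precede the first dose.

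**The concern.** An exclusion protects a patient only if it can be checked before the exposure. VIII depends on a result from the day of surgery, while one permitted enoxaparin regimen begins many hours before surgery, often on the previous evening. A patient must be allocated before receiving the allocated drug, so in that case the check also comes after randomisation.

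At stake is the safety of a patient who stopped warfarin a few days earlier and whose INR is still above 1.5. That patient could receive 40 mg of enoxaparin before the protocol's own criterion says not to enrol. Major bleeding is counted from the first dose, so the patient would already be in the safety window when found ineligible. Rivaroxaban starts after surgery, so the problem cannot arise in that arm.

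**Working it through.** The plan gives no figure to reproduce. The check is clock arithmetic, followed by an illustration of size on assumed inputs.

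**Step 1. Order of dose and INR.** Let the operation start T hours after midnight, and read the day of surgery as the calendar day, so that the INR cannot be taken before 00:00.

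- 9 to 15 hour window: the dose falls between T − 15 and T − 9. All permitted times are on the previous day when T − 9 < 0, that is, T < 9. Some are when T − 15 < 0, that is, T < 15.
- At least 12 hours before: the latest dose is at T − 12, so all permitted times are on the previous day when T < 12. The table gives no upper limit for this option, so a previous-day dose stays possible for later operations as well.

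For T from 9 to 15, the share of the 9 to 15 hour window before midnight is (15 − T)/6. It equals the share of patients only if dose times are spread evenly over the window, which is an assumption.

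| Operation | 9 to 15 h window | Share before midnight | Latest dose, at least 12 h before |
|---|---|---|---|
| 08:00 | 17:00 to 23:00, previous day | 100% | 20:00, previous day |
| 10:00 | 19:00, previous day, to 01:00 | 5/6 = 83% | 22:00, previous day |
| 12:00 | 21:00, previous day, to 03:00 | 3/6 = 50% | 00:00 |
| 14:00 | 23:00, previous day, to 05:00 | 1/6 = 17% | 02:00 |
| 15:00 | 00:00 to 06:00 | 0% | 03:00 |

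If both limits apply (12 to 15 hours), the order is forced before 12:00. The share is then (15 − T)/3: 67% at 13:00, 33% at 14:00 and 0% at 15:00. Even when the dose falls on the day of surgery, nothing in the text requires the INR to come first.

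**Step 2. Do other provisions require an earlier INR?**

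- III removes only therapy that cannot be stopped, so a patient who has stopped warfarin passes.
- V has no look-back period. Read broadly it could remove most past warfarin users; read narrowly, few.
- VI has no timing limit and can be applied early, but it is a judgement and names no INR.
- The open-ended list and the physician's decision before enrolment allow an earlier INR but do not require one.

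**Step 3. Size, on assumed inputs.** The plan's minimum of 100 patients, taken as split equally, gives 50 on enoxaparin. Assume:

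- 0% to 5% recently stopped warfarin and pass III, V and VI;
- 10% to 30% of these have an INR above 1.5;
- 50% to 100% of those are dosed the day before.

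Expected patients dosed with a raised INR:

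- Maximum: 50 × 0.05 × 0.30 × 1.0 = 0.75. Minimum: 0.
- Mid-range: 50 × 0.025 × 0.20 × 0.75 = 0.19.
- If only half start pre-operatively: 0.75 × 0.5 = 0.375 at the maximum and 0.19 × 0.5 = 0.09 at mid-range. If none do: 0.

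Chance of at least one such patient, 1 − (1 − p)^50:

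- p = 0.05 × 0.30 × 1.0 = 0.015 gives 0.53.
- p = 0.025 × 0.20 × 0.75 = 0.00375 gives 0.17.
- p = 0.00375 × 0.5 = 0.001875 gives 0.09.

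With an assumed 2% to 10% major-bleed risk in such a patient, the maximum of 0.75 patients gives 0.75 × 0.02 = 0.015 to 0.75 × 0.10 = 0.075 expected bleeds. This is total risk, not the excess due to the early dose. One bleed in 50 against none in 50 gives a two-sided Fisher exact p of 1.0.

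**The case against.** The strongest reply is that the patient at risk may not be eligible. Read literally, V covers an ordinary warfarin user without any INR. One can answer that VIII would then be almost redundant, so some warfarin users must be eligible. That inference is only moderate, because the list repeats itself elsewhere: I and IV both exclude severe hypersensitivity to the study drugs. This part of the objection stands. V is ambiguous and may already close most of the gap.

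Second, the pre-operative start is only one option, and the physician may choose another. This also stands, and it is why the point is conditional. The exposure disappears if the start is post-operative.

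Third, VIII might be a check of fitness for surgery, not a bar to the study drug. This is not persuasive, because the lead-in ties the list to drug-label contraindications. Table 1 does allow enoxaparin to continue until warfarin anticoagulation is adequate, but that concerns later treatment and not a first dose before surgery.

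Fourth, the size rests wholly on assumptions. That is correct. The 53% needs every input at its maximum, and the 17% assumes that every enoxaparin patient starts pre-operatively.

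**Conclusion.** The point holds as a minor improvement for the sponsor to consider. Under a pre-operative start, the protocol permits enoxaparin before exclusion VIII can be checked. The order is forced for operations before 09:00 (before 12:00 with the 12-hour option) and possible up to 15:00 under the 9 to 15 hour window. Nothing else in the text requires an earlier INR. The conclusion assumes that the day of surgery means the calendar day and that some patients who stopped warfarin pass III, V and VI.

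The number affected is unknown: probably well under one patient, and possibly none.

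A reader might infer more than the documents support:

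- That patients with a raised INR will be dosed. The text permits it but does not make it likely, and V, VI or the physician may prevent it.
- That the arms become non-comparable because only enoxaparin is affected. At under one expected patient and at most 0.075 expected bleeds, there is no material effect on the comparison.
- That only operations before 09:00 matter. That is where the order is forced under the 9 to 15 hour window; it is not the limit of the problem.

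**What to change.** Reword VIII. Any patient, in either arm, who took warfarin within a stated look-back (for example 14 days, to be set by the clinicians) must have an INR of 1.5 or less resulted before randomisation and before any study dose. The result should fall within a stated limit, such as 24 hours before the first possible dose. Applying the rule to both arms keeps eligibility the same for each. Keep the day-of-surgery INR only as a clinical check for delaying surgery or withholding doses, not as an exclusion after randomisation.

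The alternative is to fix the post-operative enoxaparin start of at least 12 hours that Table 1 already cites. A day-of-surgery INR taken before the operation then precedes every dose in both arms.

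The cost of rewording is possibly one earlier blood test in a few patients, and the occasional loss of a patient whose INR is still falling and would have been acceptable on the day. No change to the analysis set is proposed here. How to handle patients found ineligible after randomisation should be settled together with exclusions X (ICU stay after surgery) and XII (renal failure at any point in the study), which raise the same question.
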